#### 8.2.4 **Efficacy analysis**

For the patient efficacy analysis, the following will be studied on completion of the firstline treatment or else on the date of the patient's last follow-up when the cut-off is decided:

- Number of treatment cycles received, presenting the frequency distribution of  $\dot{\mathbf{x}}$ patients according to the number of cycles of treatment with the tyrosine kinase inhibitor in first line.
  - 0 1 2
  - 0 0
  - 3 4 0

  - 5 0 6
  - 0

CT24-GSOP-SD-GL04 NI Study SAP Template; Template Version 1.0, Effective 31-Dec-2013 Page 20 of 29 o ...

- Best response rate achieved, presenting the frequency distribution of the patients based on the best response achieved with tyrosine kinase in first line.
   CR
  - $\circ$  PR
  - o PR o SD
  - 0 SD
  - o DP
- **ORR**, the absolute and relative frequency of patients who have achieved an objective response rate will be given (CR+PR).
- ✤ CBR, the absolute and relative frequency of patients who have achieved a clinical benefit rate will be given (CR+PR+SD).
- DOR, for the sub-population of patients who have achieved ORR, the time from the date of the response to the date of progression will be calculated, providing the value of the mean, standard deviation, median, range, interquartile range and 95% confidence interval.
- Time to the best response, calculated as the difference between the treatment start date and the date on which the best response is achieved. Providing the main measures of centrality and dispersion.
- Time on treatment, calculated as the difference between the treatment start date and the treatment end date or the date of the last follow-up if the patient is still on first-line at the time of the cut-off. It will be studied using the value of the mean, standard deviation, median, range, interquartile range and 95% confidence interval.
- Reason for terminating treatment, providing the frequency distribution of the patients according to the reason for terminating the treatment:
  - Unacceptable toxicity
  - Progression
  - o Death
  - o Other
- Time to Treatment Failure (TTF). TTF will be studied by means of a Kaplan Meier survival analysis, calculated as the time elapsed from the start of treatment with a tyrosine kinase inhibitor to tumour progression, treatment discontinuation for any reason or death from any cause.
- Progression-Free Survival (PFS) Progression-free survival will be studied by means of a Kaplan Meier survival analysis, calculated as the time elapsed from the date of the start of treatment with a tyrosine kinase inhibitor to the date of progression/death, if the event occurs, or else it will be censored on the date of

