#### 6.1 EFFICACY/EFFECTIVENESS OBJECTIVES

- Progression-Free Survival (PFS): PFS will be studied using Kaplan Maier survival curves, considering progression/death as the event and time to event as the interval from the start of treatment until the first date that progressive disease (PD) is observed according to RECIST criteria (Version 1.1) or until *death*. Patients who have not had an event at the time of the analysis of the study data will be censored on the date of the last available follow-up.

- Objective Response Rate (ORR): defined as the proportion of subjects who achieve complete remission (CR) or partial response (PR). Additionally, the patients with stable disease (SD) will be evaluated. The subjects will be evaluated in accordance with RECIST criteria (Version 1.1).

- Duration of response (DOR): in patients with PR or CR, it will be defined as the interval from the date the response is documented to the first date that progressive disease is observed.

\_Time to Treatment Failure (TTF), defined as the time from the start of treatment with a tyrosine kinase inhibitor to tumour progression, treatment discontinuation for any reason or death from any cause.

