#### 7 HANDLING OF MISSING DATA

No criterion for replacing missing values will be used.

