#### 8 STATISTICAL ANALYSIS AND METHODOLOGY

#### 8.1 STATISTICAL METHODS

The investigator will collect data from the enrolled patients in an electronic Case Report Form specially designed for this study.

The patient number we provide is a serial number devoid of any identifying value.

The information is stored in an Access database, which in turn is associated with a file, "WorkGroup", detailing the user code and permits of the investigator within the database. People not within this working group cannot access the database.

A Data Management Plan (DMP) will be developed and once approved by the person responsible for the study, the "Queries" will be programmed in the electronic case form so that when the investigator saves the data, it informs him/her of any doubts regarding the data.

All changes made by the investigators during the collection of data will be stored in a table specially designed for this purpose, indicating the user, date, modified field, the old value and the new value.

The fatigue-related quality of life of the patients and the quality of life of patients with palmar-plantar erythrodysaesthesia (hand-foot syndrome) will be studied using the mean, standard deviation and confidence intervals if they follow normal distribution, or the median, minimum, maximum and interquartile range if they do not follow Gaussian distribution. The Wilcoxon test will be used to analyse the inter-visit correlation for patients' quality of life.

The objective response rate according to RECIST version 1.1 will be studied using absolute and relative frequencies.

In order to study the impact of drug administration time, napping, temporary interruptions and dose reductions on fatigue and hand-foot syndrome control, independent samples will be compared using Pearson's chi-square test (or Fisher's exact test for 2x2 tables or likelihood ratio test for mxm tables, if necessary) in the case of qualitative variables and Student's t-test, one-way ANOVA test or non-parametric equivalents, such as the Mann-Whitney U test or Kruskal-Wallis H test in the case of quantitative variables.

The Kaplan-Meier survival estimate will be used to study both the PFS and TTF of patients. The log-rank test will be used to compare the survival distributions.

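### Duration of response is summarised with a plain mean, SD, median and 95% CI and has no censoring rule, so responders who have not progressed shorten the mean and can shorten the median.

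*SAP*

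**What the plan says.** SAP 6.1 defines DOR, in patients with CR or PR, as "the interval from the date the response is documented to the first date that progressive disease is observed". SAP section 6 and protocol 7.3 give the same definition in substance. SAP 8.2.4 then states the analysis: "the time from the date of the response to the date of progression will be calculated, providing the value of the mean", followed by SD, median, range, interquartile range and a 95% CI.

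Four other places bear on responders who have not progressed:

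- The opening of SAP 8.2.4 says the efficacy items are studied when first-line treatment is complete or at the patient's "last follow-up when the cut-off is decided".
- SAP 7 says "No criterion for replacing missing values will be used".
- SAP 8.1, like protocol 7.7, says "The Kaplan-Meier survival estimate will be used to study both the PFS and TTF of patients". DOR is not named.
- A censoring date is written for PFS only. Patients without an event "will be censored on the date of the last available follow-up" (SAP 6.1), and SAP 8.2.4 repeats the rule.

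**The concern.** DOR is a time-to-event variable, and the plan treats it as a fully observed measurement. The text leaves two ways to handle a responder with no progression date, and the analyst would have to choose between them with the data in hand:

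- **Dropped.** The interval cannot be calculated, and SAP 7 rules out replacing it. The summary then covers only responders who progressed early enough to be seen.
- **Last follow-up as end date.** The opening of SAP 8.2.4 could be read this way. An ongoing response is then counted as if it had ended.

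Such patients are to be expected. SAP 8.2.4 provides for patients still on first-line treatment at the cut-off. Its reasons for ending treatment include "Unacceptable toxicity" and an other category, neither of which produces a progression date. The report would set a DOR that ignores censoring beside a PFS that censors the same patients.

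**Working it through.** The documents give no DOR figure, number of responders or target precision, so there is no stated result to reproduce.

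**Direction.** Let T be the true DOR and C the follow-up after response, independent of T.

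- Last follow-up: the recorded value is min(T, C), which never exceeds T. The mean is too short as soon as one responder is censored. The median solves P(T>t)·P(C>t) = 0.5, so it is unchanged only if no censoring occurs before the true median.
- Dropped: the recorded values follow T given T ≤ C. This weights each duration t by P(C ≥ t), which falls as t grows, so mean and median both move down.

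**Inputs for size.**

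- First patient February 2016, 18 months of recruitment and data collection to May 2018, that is, month 27 (protocol section 3, Schedule). Uniform accrual is assumed.
- Response at month 3, the time of the first control CT (protocol 7.2). This is an assumption.
- Exponential DOR with median m = 4 to 14 months, and no death without progression. These are assumptions; the nearest time scale in the documents is the 11-month median PFS for sunitinib in protocol section 5.

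Hence C = 27 − U(0, 18) − 3, uniform from a = 6 to b = 24 months.

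**Worked case, m = 11.** λ = ln 2 / 11 = 0.06301, so the true mean is 1/λ = 15.87.

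- Unprogressed share: q = (e^(−6λ) − e^(−24λ)) / (18λ) = (0.6852 − 0.2204) / 1.134 = 0.41.
- Mean with last follow-up: (1 − q)/λ = 0.590 × 15.87 = 9.4. For an exponential DOR the proportional shortfall equals q.
- Mean if dropped: [(1 − q)/λ − E(C; T>C)] / (1 − q), where E(C; T>C) = [(a/λ + 1/λ²)e^(−λa) − (b/λ + 1/λ²)e^(−λb)] / (b − a) = (347.1 × 0.6852 − 632.7 × 0.2204) / 18 = 5.46. This gives (9.37 − 5.46) / 0.590 = 6.6.
- Median with last follow-up: e^(−λt)·(24 − t)/18 = 0.5 gives t = 8.6. Median if dropped: 5.6.
- Kaplan-Meier on the same simulated data, in a large sample: 11.0.

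**Range.** Change from the true value:

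| Accrual | True median | Unprogressed | Mean, dropped | Mean, last follow-up | Median, dropped | Median, last follow-up |
|---|---|---|---|---|---|---|
| 18 mo | 4 | 11% | −23% | −11% | −15% | 0% |
| 18 mo | 6 | 21% | −37% | −21% | −28% | 0% |
| 18 mo | 8 | 30% | −48% | −30% | −38% | −10% |
| 18 mo | 11 | 41% | −58% | −41% | −50% | −22% |
| 18 mo | 14 | 49% | −66% | −49% | −58% | −32% |
| 12 mo | 4 | 5% | −15% | −5% | −7% | 0% |
| 12 mo | 6 | 14% | −30% | −14% | −18% | 0% |
| 12 mo | 8 | 22% | −41% | −22% | −29% | 0% |
| 12 mo | 11 | 33% | −53% | −33% | −41% | 0% |
| 12 mo | 14 | 42% | −61% | −42% | −50% | −9% |

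The zeros follow from the shortest follow-up after response: 27 − 18 − 3 = 6 months, or 27 − 12 − 3 = 12 months.

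**Sensitivity, 18-month accrual.** Response at month 6 moves the median by −24% to −64% (dropped) or −6% to −44% (last follow-up). Weibull shapes 0.8 and 1.5 give −4% to −66% or 0% to −34%. Over all runs, at either accrual length, the mean was short by between under 1% and 76%.

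**Interval.** With an assumed 30 responders, 18-month accrual and a true median of 6 months, the nominal 95% CI contains the true mean in about 13% (dropped) or 54% (last follow-up) of samples, against 93% without censoring.

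**After the fix.** Kaplan-Meier medians with 30 responders were typically within about 5% of the truth in all ten exponential cases. The median was not reached in 12% of samples at a true median of 14 months with 18-month accrual.

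**The case against.** The gap in the text is not disputable; its weight is. DOR is not among the seven secondary objectives, protocol 7.7 does not mention it, and no decision rests on it. PFS and TTF, which are objectives, already have Kaplan-Meier. That limits the importance of the point but does not make the planned summary correct.

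The last-follow-up reading has thin support. In the same list, time on treatment is expressly given the last follow-up as its end date and DOR is not, which favours dropping. This stands, and dropping is the reading with the larger bias.

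Data collection may also close before May 2018, once the last patient has moved to second-line therapy (protocol section 3, Schedule). Few responders would then be censored by the calendar, and the bias would be smaller than in the table, which fixes the cut-off at month 27. This also stands. Patients who changed treatment for toxicity could still lack a progression date.

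The model contains only calendar censoring. With early stops or losses to follow-up, the shortest follow-up after response could fall below 6 or 12 months, so the 0% entries are not a guarantee.

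Finally, the coverage figures refer to the unrestricted exponential mean, which a Kaplan-Meier median does not estimate. They show that the mean is a poor summary here; they do not measure the gain from the fix.

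**Conclusion.** The concern holds. Followed as written, SAP 8.2.4 gives a mean DOR that is too short under either reading whenever a responder is censored, and a median that is too short if such patients are dropped and may be too short otherwise. For the last-follow-up mean the direction needs no assumption. For the dropped reading it needs censoring unrelated to DOR.

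The size is illustrative. Over assumed true medians of 4 to 14 months, the exponential cases with response at month 3 put the mean 5% to 66% short and the median 0% to 58% short, depending on accrual and on the reading. Early closure would reduce these figures. The point deserves correction before analysis, but it concerns a supporting efficacy description and leaves the primary objective untouched.

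**What to change.** In SAP 8.2.4, estimate DOR by Kaplan-Meier in all patients with CR or PR, from the response date to first progression, and censor patients without progression at last available follow-up, as SAP 6.1 does for PFS. Report the median, its 95% CI and the numbers of events and censored patients, in place of the simple mean, SD and CI. Add DOR to the Kaplan-Meier sentence in SAP 8.1.

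Two rules should be stated at the same time: whether death without progression is an event or is censored, and whether follow-up after the start of second-line treatment counts towards DOR.

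The cost is wording in SAP 8.1 and 8.2.4. The SPSS procedure is already planned for PFS and TTF, and no new data are needed. The DOR definitions in protocol 7.3 and SAP 6 and 6.1 change only if death is made an event.

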#### 5 ANALYSIS POPULATION

#### 5.1 FULL ANALYSIS SET

Plans are to include 100 patients in the study to receive first-line treatment over the course of 18 months at 35 sites.

This is a descriptive study; therefore, a specific number of patients is not required to calculate the sample size.

In order to study the fatigue-related quality of life of patients who are taking a tyrosine kinase inhibitor, evaluated using the validated 13-item FACIT-Fatigue scale for patients with metastatic renal cancer on Spanish, the inclusion of 100 patients with metastatic renal carcinoma who are about to receive first-line treatment with a tyrosine kinase inhibitor and who meet the screening criteria of the study is proposed.

This sample size will allow us to estimate percentages of patients with fatigue (severe/non-severe) during follow-up, with a 95% level of significance and an estimated proportion of 10%, assuming a discontinuation rate of 5%.

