#### TREATMENT

- 1) Time when the oral treatment is taken
- 2) Tyrosine kinase inhibitor dose and treatment regimen
- 3) Number of dose changes per treatment cycle
- 4) Temporary treatment interruptions, number of interruptions per treatment cycle
- 5) Best response achieved with first-line treatment
- 6) Mean duration of treatment
- 7) Time to treatment failure
- 8) How long each patient stays on first-line treatment/no. of cycles received
- 9) Reason for discontinuing the first-line drug
- 10) Date of disease progression and/or death

Through the analysis of the collected variables the following aspects will be assessed:

- **Progression-Free Survival (PFS):** defined as the interval from the start of treatment to the date of the first documentation of objective tumour progression or death from any cause.

- **Objective Response Rate (ORR):** Defined as the proportion of subjects who achieve complete remission (CR) or partial response (PR). In addition, subjects with stable disease (SD) will also be evaluated to obtain clinical benefit along with subjects with tumour progression. Subjects will be evaluated according to RECIST 1.1.

- **Duration of response (DOR):** in patients with PR or CR, it will be defined as the interval from the date the response is documented to the first date that progressive disease is observed.

- **Safety:** The safety of the tyrosine kinase inhibitor will be evaluated describing the incidence and all grades in the event of fatigue and or hand-foot syndrome.

- **Fatigue-related quality of life of patients:** this will be measured based on the results obtained after completion of the FACIT-Fatigue questionnaire by the patient.

- **HFS-related quality of life of patients** in cases in which HFS is present with a score from 1 to 3 according to version 4 of the CTCAE (Common Terminology Criteria for Adverse Events).

- Date of disease progression and/or death.

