	.4	Association between daytime dose changes and evolution on the Facit_Fatigue (every six weeks)
	.5	Association between doses, daytime treatment regimen and evolution on the Facit_Fatigue (every six weeks)
	.6	Association between temporary daytime interruptions and evolution on the Facit_Fatigue (every six weeks)
.4	5	Treatment, dose changes and temporary interruptions
· ·	7	Efficacy analysis
	.1	Number of treatment cycles received
	.2	Best response rate achieved with first-line treatment
	.3	ORR, DOR
	.4	Time on treatment and time to best response
	.5	Time to Treatment Failure (TTF)
	.6	Progression-free survival (PFS)
	.7	Reason for termination of treatment and reason for death

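### Time on treatment counts patients still on their TKI as finished at last follow-up, so the planned mean, upper quartile and confidence interval understate treatment duration; the median is little affected

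*SAP*

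**What the plan says.** SAP 8.2.4 defines time on treatment as the interval from treatment start to treatment end. For patients who have not stopped, the end point becomes "the date of the last follow-up if the patient is still on first-line at the time of the cut-off". On the analysis it says: "It will be studied using the value of the mean, standard deviation, median, range, interquartile range and 95% confidence interval". It gives no censoring indicator and no survival method for this variable.

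The result is listed as a study variable, "Mean duration of treatment", in SAP section 6 (Treatment) and under the same label in Protocol 7.3. In the SAP section 9 table list it appears under efficacy as "Time on treatment and time to best response".

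Other time variables with the same follow-up are handled differently. For time to treatment failure, SAP 8.2.4 says "TTF will be studied by means of a Kaplan Meier survival analysis". For PFS, SAP 6.1 says that patients without an event "will be censored on the date of the last available follow-up", and SAP 8.2.4 repeats that rule. SAP 8.1 names only two variables for the survival method: "The Kaplan-Meier survival estimate will be used to study both the PFS and TTF of patients".

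**The concern.** The last follow-up date is a censoring date for PFS but a completed end of treatment for time on treatment. An ongoing patient's true duration is longer than the value entered, by an unknown amount, and a plain mean ignores this.

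The SAP wording provides for such patients, and the calendar makes them likely. Recruitment is planned from February 2016 to August 2017 and data collection ends by May 2018, so the last patients recruited have about 9 months of follow-up. The bias disappears only if nobody remains on first-line treatment at the cut-off.

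The study's rationale rests on tolerability and on keeping patients on dose, so readers will use the treatment duration it reports. A mean that is too short, with a narrow 95% CI around it, would be quoted as a finding.

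**Working it through.** **Planned figure.** The documents state no expected time on treatment, so there is nothing to reproduce. The size below rests on assumptions; the direction does not.

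**Direction.** Let T be the true time on treatment and C the time from treatment start to the cut-off. The SAP value is X = min(T, C), which never exceeds T. The mean of X is therefore below the mean of T whenever anyone is ongoing, whatever the distribution.

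**Inputs**
- n = 100 (SAP 5.1: "Plans are to include 100 patients in the study to receive first-line treatment over the course of 18 months at 35 sites").
- Follow-up of 9 to 27 months: August 2017 to May 2018 is 9 months and February 2016 to May 2018 is 27 months (Protocol section 3, Schedule). Uniform accrual is assumed.
- Scale: the background sections quote median PFS of 11 months (sunitinib) and 9.2 months (pazopanib). These are borrowed as assumed medians for time on treatment. A median of 6 months is added for more frequent early stopping.
- Exponential T (assumed).

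**Formulas**, with λ = ln 2 / median:
- Fraction ongoing: p = (e^(−9λ) − e^(−27λ)) / (18λ)
- Planned mean: M = (1 − p) / λ
- Mean restricted to 27 months: R = (1 − e^(−27λ)) / λ

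The comparator is R because 27 months is the longest possible follow-up.

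**Worked case, median 9.2.** λ = 0.6931 / 9.2 = 0.0753. Then e^(−9λ) = 0.508 and e^(−27λ) = 0.131, so p = 0.377 / 1.356 = 0.278. M = 0.722 / 0.0753 = 9.6 months and R = 0.869 / 0.0753 = 11.5 months. The shortfall is 1 − 9.58/11.54 = 17%.

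| Assumed true median (months) | 6 | 9.2 | 11 |
|---|---|---|---|
| Still on treatment | 15% | 28% | 34% |
| Planned mean | 7.4 | 9.6 | 10.5 |
| Mean restricted to 27 months | 8.3 | 11.5 | 13.0 |
| Shortfall | 11% | 17% | 19% |
| Planned median | 6.0 | 9.1 | 10.0 |
| Planned upper quartile | 11.0 | 14.0 | 15.2 |
| True upper quartile (2 × median) | 12.0 | 18.4 | 22.0 |

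The planned median and upper quartile solve P(X > t) = 0.5 and 0.25. Here P(X > t) = e^(−λt) up to 9 months and e^(−λt)(27 − t)/18 after that. For example, at median 11 and t = 15.24, 0.383 × 0.653 = 0.25.

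**Confidence interval.** The SD of X is 5.87, 6.66 and 6.86 months, so the half-width 1.96 × SD/10 is 1.15, 1.31 and 1.34 months. The shortfall R − M is 0.91, 1.95 and 2.49 months, or 1.54, 2.93 and 3.63 standard errors. Approximate coverage of R is Φ(1.96 − 1.54), Φ(1.96 − 2.93) and Φ(1.96 − 3.63), that is 66%, 17% and 5%. Simulation with n = 100 gives about 65%, 18% and 5%.

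**Kaplan-Meier on the same data.** With ongoing patients censored at last follow-up, the average estimated median in simulation is 6.0, 9.2 and 11.0 months, matching the assumed values.

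**The case against.** **Time to treatment failure already covers this.** It is a stated secondary objective, counts stopping for any cause as an event and is analysed by Kaplan-Meier. Time on treatment is not among the seven secondary objectives. This stands as a limit on the consequence. But treatment failure also counts progression, even if the drug continues, and its own censoring rule is not written out. It does not correct the separately listed duration.

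**The quantity can be read as observed exposure to cut-off.** SAP 8.2.4 opens by saying that its items are studied at the end of first-line treatment or at last follow-up. On that reading the mean is right for what it measures, and the defect is the label and the missing count of ongoing patients. That is why relabelling is acceptable as a second choice. As written, the result sits under efficacy, is called a mean duration and carries a 95% CI.

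**The median is also planned.** True, and it is close to right. The distortion is in the mean, SD, upper quartile, maximum and CI.

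**The scale is borrowed.** PFS medians stand in for time on treatment. Stopping for toxicity would shorten it and reduce the bias; treatment past progression would do the opposite.

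**Stronger readings that do not hold**
- A reader might compare the planned mean with the full exponential mean: 8.7, 13.3 and 15.9 months, or shortfalls of 15%, 28% and 34%, with coverage near zero at the two longer medians. No analysis of at most 27 months' follow-up can estimate that mean without extrapolating an assumed distribution.
- A reader might infer that those who tolerate the drug longest are cut shortest. Under staggered entry, the shortest follow-up belongs to the last recruited.
- A reader might extend the point to cycles received. That is a true count of cycles given by the cut-off.
- Time on treatment does not have a table to itself; its entry is shared with time to best response.

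**Conclusion.** The concern holds for the mean, upper quartile and CI when read as estimates of treatment duration. The cause is a stated rule in SAP 8.2.4, not a missing sentence. The direction is certain if anyone is ongoing at cut-off. The size is moderate: a shortfall of 11% to 19% against a 27-month restricted mean for true medians of 6 to 11 months, with CI coverage falling from about 65% to about 5%. These figures depend on exponential times, uniform follow-up of 9 to 27 months and borrowed medians.

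The documents do not support saying that the whole time-on-treatment summary is invalid: the planned median is within about 1 month of the truth in every case examined. Nor is the primary objective touched. This is a predictable bias in a secondary descriptive result, worth correcting before the analysis.

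**What to change.** In SAP 8.2.4, analyse time on treatment by Kaplan-Meier. The event is permanent stop of the first-line TKI for any reason, including death; patients still on treatment are censored at last follow-up. Report the median with 95% CI, the number still on treatment, and a restricted mean to a horizon stated in advance. Nine months is one the planned schedule allows every patient to reach; a longer horizon rests on fewer patients. Change the variable label in SAP section 6 and Protocol 7.3 to match.

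If the plain summary is kept, call it observed exposure to cut-off and show the number ongoing beside it.

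The cost is a few lines of SAP text and one more Kaplan-Meier table from dates already collected. The downside is that an unrestricted mean duration can no longer be quoted. A 9-month restricted mean will also be a smaller number than the planned mean (6.9 against 10.5 months at an assumed median of 11), so the horizon must be reported with it.
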